## **2.2 Medtronic Transcatheter Aortic Valve Replacement System**

The Medtronic Transcatheter Aortic Valve Replacement (TAVR) system in this trial includes the following TAVR systems:

### **2.2.1 Evolut R system**

The Evolut R System is a recapturable transcatheter aortic valve replacement system comprised of the following three components:

1. Evolut R Transcatheter Aortic Valve (TAV)
2. EnVeo R Delivery Catheter System (DCS) with EnVeo InLine Sheath or EnVeo PRO Delivery Catheter System (DCS)
3. EnVeo R Loading System (LS) or EnVeo PRO Loading System (LS)

### **2.2.2 Medtronic Evolut PRO System**

The Medtronic Evolut PRO System is a transcatheter aortic valve replacement system comprised of the following three components:

1. Medtronic Evolut PRO Transcatheter Aortic Valve (TAV)
2. Medtronic Evolut PRO Delivery Catheter System (DCS) with InLine Sheath or EnVeo R Delivery Catheter System (DCS) with EnVeo InLine Sheath or EnVeo PRO Delivery Catheter System (DCS)
3. Medtronic Evolut PRO Loading System (LS) or EnVeo PRO Loading System (LS)

The Evolut R and Evolut PRO TAV treat aortic stenosis by displacing and functionally replacing the dysfunctional native valve with a bioprosthetic valve delivered on a catheter while the heart is still beating, thus avoiding the risks of cardiopulmonary bypass. Their intended performance is to relieve aortic valve stenosis without inducing significant regurgitation, thereby restoring effective aortic valve function.

A detailed description of the Evolut R and Evolut PRO systems are provided in Section 5.0 Description of Investigational Devices.

### **2.3 Intended Use**

Data from this trial will be used to support an expansion of the currently approved indication to include patients with aortic stenosis who are indicated for aortic valve replacement and are deemed at low predicted risk for mortality for SAVR, where low risk is defined as predicted risk of mortality for SAVR <3% at 30 days per multidisciplinary local heart team assessment.

## 2.4 Trial Objectives

### 2.4.1 Primary Objective

The primary objective of this trial is to demonstrate that the safety and effectiveness of the Medtronic TAVR systems, as measured by the rate of all-cause mortality or disabling stroke at 2 years, is non-inferior to SAVR in the treatment of severe aortic stenosis in subjects who have a low predicted risk of mortality at 30 days for SAVR.

### 2.4.2 Exploratory Objective

An exploratory objective is to evaluate the incidence of findings of prosthetic valve leaflet thickening or leaflet immobility (LTI) by Multi Detector Computed Tomography following TAVR with the Medtronic TAVR system or SAVR with commercially available surgical bioprostheses.

## 2.5 Trial Endpoints

The following endpoints will be used to evaluate the primary trial objectives:

### 2.5.1 Primary Safety and Effectiveness Endpoint

- The rate of all-cause mortality or disabling stroke at 2 years

### 2.5.2 Secondary Safety Endpoints

- The rate of the composite of death, disabling stroke, life-threatening bleed, major vascular complication, or AKI (II or III) at 30 days
- The rate of new permanent pacemaker implantation at 30 days
- The rate of prosthetic valve endocarditis at one year
- The rate of prosthetic valve thrombosis at one year
- The rate of all stroke (disabling and non-disabling) at one year
- The rate of life-threatening bleeding at one year
- The rate of valve-related dysfunction requiring repeat procedure at one year

### 2.5.3 Secondary Effectiveness Endpoints

- The rate of valve-related dysfunction, defined as moderate or severe prosthetic valve stenosis, or moderate or severe prosthetic regurgitation at one year (per VARC II)
- Quality of Life as assessed by Kansas City Cardiomyopathy (KCCQ) at 30 days and one year
- The rate of repeat hospitalization for aortic valve disease at one year
- Device Success (VARC II), defined as
  - Absence of procedural mortality, AND
  - Correct positioning of a single prosthetic heart valve into the proper anatomical location, AND
  - Intended performance of the prosthetic heart valve, defined as the absence of patient-prosthesis-mismatch and mean aortic valve gradient less than 20 mmHg (or peak velocity <3 m/sec), AND absence of moderate or severe prosthetic valve regurgitation.
- Hemodynamic performance metrics by Doppler echocardiography

- Mean aortic gradient at one year
- Effective orifice area at one year
- Degree of total, peri, and transvalvular prosthetic regurgitation at one year
- New York Heart Association (NYHA) functional classification at one year
- Health-related quality of life at one year as assessed by EQ-5D survey instrument

## **2.7 Rationale for Selection of Trial Endpoints**

The basis for the selection of these endpoints includes the following considerations:

- They are clinically relevant and address important safety and effectiveness aspects of the Medtronic TAVR System compared to SAVR.
- They are objectively defined and measurable in the majority of subjects.
- They are consistent with current recommendations for endpoints in TAVR clinical studies.

### 3.0 TRIAL PROTOCOL

#### 3.1 Ethics and Regulatory Compliance

##### 3.1.1 Applicable Regulations

This trial was designed to reflect the Good Clinical Practice (GCP) principles outlined in ISO 14155:2011. These include the protection of the rights, safety and well-being of human subjects, controls to ensure the scientific conduct and credibility of the clinical investigation and the definition of responsibilities of the sponsor and investigators.

The trial will be conducted according to federal, national and local laws, regulations, standards, and requirements of the countries/geographies where the trial is being conducted. The trial will also be conducted in accordance with the Declaration of Helsinki. The principles of the Declaration of Helsinki are implemented in this trial by means of the Patient Informed Consent (IC) process, Ethics Board approval, trial training, clinical trial registration, pre-clinical testing, risk benefit assessment, and publication policy.

In the United States, the trial will be conducted under an FDA Investigational Device Exemption (IDE) in compliance with 21 CFR Parts 11, 50, 54, 56 and 812, and ISO 14155:2011. In addition, the trial will be conducted in compliance with 21 CFR Part 11 and 54 in all participating geographies. In Europe and Canada, the trial will be conducted in compliance with ISO 14155:2011. In Canada, SOR/98-282, Section 79-88 will also be followed. In Europe, MDD 93/42/EEC and MEDDEV 2.7/3 will also be followed. In Australia and New Zealand the trial will be conducted in compliance with local regulations and ISO 14155:2011. In Japan, the trial will be conducted in accordance with the ethical principles of the Japan GCP Ordinance, the Pharmaceutical and Medical Device Act as well as ISO 14155:2011.

Regulatory authority notification/approval to conduct the trial is required in all participating geographies. Investigational sites will not be activated, nor begin enrolling subjects until the required approval/favorable opinion from the respective regulatory agency has been obtained (as appropriate). Additionally, any requirements imposed by a local regulatory agency or Ethics Board shall be followed, as appropriate.

This trial will be publicly registered prior to first enrollment in accordance with the 2007 Food and Drug Administration Amendments Act (FDAAA) and Declaration of Helsinki on <http://clinicaltrials.gov> (PL 110-85, Section 810(a)).

##### 3.1.2 Institutional Review Board and Ethics Committee

The trial will be conducted in accordance with the requirements of local Institutional Review Boards and Ethics Committees. The responsible Institutional Review Board (IRB) or Ethics Committee (EC) at each investigational site must approve the trial protocol and informed consent form. Trial activities will not commence prior to receipt of documentation of IRB/EC approval by the site and Medtronic. The Investigator and trial staff must comply with the requirements of their IRB/EC, including any additional requirements imposed by the IRB/EC after initial approval.

Prior to enrolling subjects, each investigation site's IRB/EC will be required to approve the current CIP, the Informed Consent form, and any other written information to be provided to the subjects. Trial sites in the

United States must also utilize IRB approved Health Insurance Portability and Accountability Act (HIPAA) Authorization.

IRB/EC approval of the clinical trial must be received in the form of a letter and provided to Medtronic before commencement of the trial at an investigation site. The approval letter must contain enough information to identify the version or date of the documents approved. In addition the approval letter needs to be accompanied by an IRB/EC roster or letter of compliance, to allow verification that the investigator, other center trial staff, and/or Medtronic personnel are not members of the IRB/EC. If they are members of the IRB/EC, written documentation is required stating that he/she did not participate in the approval process. Investigators must inform Medtronic of any change in status of IRB/EC approval once the investigation site has started enrollment. If any action is taken by an IRB/EC with respect to the investigation, that information will be forwarded to Medtronic by the respective investigator.

### **3.1.3 Regulatory Submissions**

Each site must fulfill all local regulatory requirements prior to enrolling subjects. Each study site must have written documentation of site/investigator readiness, including but not limited to IRB/EC approval of the current version of the CIP, Informed Consent form, a signed Investigator's Agreement, current investigator curriculum vitae, and documentation of training. The principal investigators and their institutions shall agree to this CIP and any amendments and indicate their approval by signing and dating the Clinical Trial Agreement.

Each center is required to have documented approval from their local Regulatory Authority prior to their first subject enrollment. Medtronic will obtain a copy of the approval letter from the Regulatory Authorities.

Other documents referred to in this CIP are listed as follows and will be made available upon request:

- Monitoring Plan
- Data Management Plan
- Statistical Analysis Plan
- Safety Plan
- Electronic Case Report Forms (eCRFs)

If a regulatory authority imposes any additional requirements (eg, safety reports, progress reports), Medtronic will prepare the required documents and send them to the respective authority.

Any revisions or amendments to the CIP, Investigator Brochure, or Informed Consent documents will be submitted to all affected Regulatory Authorities. A final report will be submitted to all Regulatory Authorities upon trial closure.

### **3.1.4 Ethical Conduct of the Trial**

The trial will be conducted in accordance with the design and specific provisions of this protocol, in accordance with the ethical principles that have their origin in the Declaration of Helsinki, and that are consistent with Good Clinical Practice (GCP) and the applicable regulatory requirements.

The principles of the Declaration of Helsinki have all been implemented by means of the patient informed consent process, IRB/EC approval, trial training, clinical trial registration, preclinical testing, risk benefit

assessment, and publication policy. Pediatric, legally incompetent, or otherwise vulnerable patients are not eligible for the trial. Further, the Medtronic TAVR system will not be used as an emergency treatment.

### **3.2 Trial Organization**

#### **3.2.1 Investigational Sites**

This trial may be conducted at up to 100 sites in the United States, Canada, Europe, Australia, New Zealand, and Japan. Investigative sites will meet the following criteria:

1. The site will have extensive experience with TAVR and SAVR, including the following:
  - cardiothoracic surgeon with either  $\geq 100$  career AVRs, or  $\geq 25$  AVRs in a calendar year
  - an interventional cardiologist with  $\geq 20$  TAVR procedures in the prior year, or  $\geq 40$  TAVR procedures in the prior two years.
2. The site will have the presence or capacity of establishing an investigative team consisting of the following:
  - interventional cardiologist with expertise in transcatheter aortic valve replacement
  - cardiothoracic surgeon with expertise in aortic valve replacement
  - echocardiographer
  - trial coordinator
3. Sites that participate in the LTI Sub-Study will have capability of performing high quality retrospective ECG gated MDCT scans, and validated CT equipment that meets minimum requirements for temporal resolution.

Information on the investigational sites (eg, name, address, PI) will be maintained in a separate document.

#### **3.2.2 Trial Site Investigative Team Members**

The following is a description of the key personnel who will form the investigative team at each trial site.

##### **3.2.2.1 Site Co-Principal Investigators**

Each site will have two Co-Principal Investigators (PI), one who is an interventional cardiologist, and one who is a cardiothoracic surgeon. The Co-PIs have overall responsibility for the conduct of the trial at the site, including protecting the rights, safety, and welfare of the study subjects at their site, the integrity of the trial data generated by their site, and for ensuring the trial is conducted in compliance with the Clinical Investigation Plan, 21 CFR 812, and IRB/EC requirements.

##### **3.2.2.2 Heart Team**

Each site will utilize a local heart team to assess eligibility of the prospective subject for the trial.

At a minimum, the local Heart Team should include the following members:

1. A cardiothoracic surgeon
2. An interventional cardiologist
3. An echocardiographer

The site Co-PIs may also serve as a member of the Heart Team.

### **3.2.2.3 TAVR Implant Team**

Each site will have a TAVR implant team with extensive experience with TAVR procedures. Operator 1 and Operator 2 must meet the minimum TAVR qualification as described in Section 3.2.1 (1).

### **3.2.2.4 Echocardiographer**

Each site will have a designated cardiologist whose primary responsibilities are to ensure the required echocardiograms are performed in accordance with the CIP, and for reviewing and approving the site echocardiography eCRFs, if authorized by the PI. The designated echocardiographer may also serve as a member of the local Heart Team.

### **3.2.2.5 Trial Coordinator**

Each site will have a designated trial coordinator whose responsibilities include coordination of trial activities, follow-up evaluations, and maintaining the records defined in the CIP.

### **3.2.2.6 Cardiovascular Imaging Specialist**

Sites that participate in the LTI Sub-Study will have a designated cardiovascular imaging specialist, whose primary responsibilities are to ensure the required MDCT images are acquired in accordance with the LTI Sub-Study protocol and for review of the acquired images. The Cardiovascular Imaging Specialist is either a radiologist or cardiologist with expertise in MDCT.

## **3.2.3 Screening Committee**

A Screening Committee will be used to ensure patient selection is appropriate and consistent among trial sites. The role of the Screening Committee will include the following:

- Confirmation that subjects are at low predicted risk of mortality at 30 days for SAVR
- Confirmation that subjects are anatomical suitable for implantation for both TAVR and SAVR

The Screening Committee will include interventional cardiologists and cardiac surgeons. Prior to the onset of the trial, the Screening Committee will establish a charter that describes its roles, responsibilities, and processes.

## **3.2.4 Publication Committee**

A Publication Committee will provide direction and support in the development of clinical publications. The Publication Committee will consist of trial investigators and Medtronic representatives. The Publication Committee will be responsible to:

- Define the publication plan
- Review, approve, and prioritize publication proposals
- Provide input on the scientific merit and clinical relevance of ancillary publications
- Identify the manuscript/abstract first author(s)/writer(s)/presenter(s)
- Review publications prior to submission

### **3.2.5 Clinical Investigational Agreement and Financial Disclosure**

A Clinical Investigation Agreement shall be signed by the participating investigation site and/or the principal investigator at each investigation center per the local legal requirements, and returned to Medtronic prior to trial center activation. The investigator is required to indicate their approval of the CIP (and any subsequent amendments), by signing and dating the agreement. All investigators will be asked to complete financial disclosure statements provided by Medtronic prior to their participation in the trial.

### **3.2.6 Curriculum Vitae**

Signed and dated curriculum vitae shall be obtained for all investigators, including their current position at the investigation site in compliance with applicable local regulations.

### **3.2.7 Trial Training**

Prior to investigational center activation or subsequent involvement in trial activities, Medtronic will provide training to the investigative team on the trial methods, procedures, and requirements. Training may be conducted via site initiation visits, investigator meetings, and/or other media sessions. Medtronic will maintain documentation of these training sessions. For new trial team members that join the trial after site activation, the PI may provide training on the trial with permission from Medtronic. Additionally, Medtronic representative(s) may be present at each site's implant procedures as part of the ongoing training process.

## **3.3 Methodology**

### **3.3.1 Patient Population**

The population includes males and females with severe aortic stenosis with a clinical indication for surgical aortic valve replacement with a bioprosthesis who are at low predicted risk of mortality at 30 days for surgical aortic valve replacement.

### **3.3.2 Trial Design**

This is a multi-center, international, prospective, randomized, interventional trial. The primary trial objective will be accomplished by 1:1 randomization to TAVR and SAVR and assessing the clinical endpoints and outcome measures described in Section 2.5. The exploratory objective will be accomplished through evaluation of the data as described in the LTI Sub-Study, APPENDIX VII: LEAFLET THICKENING/IMMOBILITY SUB-STUDY PROTOCOL.

The trial methods include the following measures to minimize potential sources of bias:

- An external, independent Screening Committee will confirm subject eligibility and anatomical suitability.
- An external, independent Clinical Events Committee (CEC) will review and adjudicate, at minimum, all deaths and endpoint related adverse events. Safety endpoint results will be based on CEC adjudications.
- All sites will follow a standardized protocol for acquisition of echocardiographic endpoint data.
- An Echo Core Lab will evaluate all echocardiograms. Echocardiographic trial endpoint results will be based on Core Lab assessments.

- Trial sites should follow their institutional procedures for maintenance of echocardiography and laboratory equipment used for assessing the trial variables.

### 3.3.3 Statistical Aspects

#### 3.3.3.1 Historical Data

Although the experience with surgical aortic valves in low surgical risk aortic valve replacement populations is extensive, it was not considered possible to leverage much of the data from these studies directly as surgical aortic valve replacement series typically enroll patient populations which include a proportion subjects with a bicuspid or unicuspid valve which may be as high as approximately 50% and also include subjects with purely or primarily regurgitant lesions (also excluded from this trial) whose outcomes may differ from patients with aortic stenosis. As a result, series for which individual patient data were available or which were known to attempt exclusion of patients with bicuspid or unicuspid valves comprise the primary basis for the event rate estimate and additional series were considered only confirmatory in nature. Table 1 presents the rates of all-cause mortality at 24 months from studies which were considered in developing the event rate estimate. The simple weighted average from the studies was 11.4% which was adjusted up to 12% to account for the possibility that surgical candidates at extremely low risk (i.e. the healthiest and youngest potential subjects) may forego randomization into a TAVR trial until longer term data and data from lower surgical risk patients are available for TAVR.

**Table 1. Surgical series supporting all-cause mortality event rate estimate**

Surgical Series	Number in cohort	24-Month all-cause mortality K-M Rate
NOTION SAVR cohort 	134	9.8%
3f Pivotal cohort 	405	12.7%
Mosaic sub-analysis 	646	9.9%
Freestyle sub-analysis 	323	13.5%
Simple Weighted Average	1508	11.4%

Entire cohort leveraged (data on file)

Sub-group analysis excluding subjects <65 years of age, with congenital bicuspid valves or with a purely regurgitant lesion

Sub-group analysis excluding subjects <65 years of age, with congenital bicuspid valves, with a purely regurgitant lesion or with the Freestyle valve implanted as a full-root replacement

The 24-month event rate estimate for non-fatal disabling stroke of 3% was generated primarily from the CoreValve US Pivotal High Risk Trial SAVR (3.9%) and TAVR (2.0%) cohorts which used event definitions consistent with this trial. Additional sources of data considered include the NOTION SAVR cohort (4.6%) and the Mosaic and Freestyle cohort sub-analyses (which had rates of 2.0% and 2.3% respectively) all of which collected clinical stroke/cerebrovascular accidents.

The expected sample size for this trial was determined based on the primary endpoint of all-cause mortality or disabling stroke at 24 months. The assumed values  $\pi_T = \pi_C = 0.15$  are based on an assumed rate of all-cause mortality of 12% at 24 months and a non-fatal disabling stroke rate of 3% at 24 months.

### 3.3.3.2 Analysis Sets

#### 3.3.3.2.1 Screening Population

All subjects with severe aortic stenosis who provide an informed consent will be considered screened and enrolled and all available data will be entered into the Electronic Data Capture (EDC) system.

#### 3.3.3.2.2 Randomized Population

If the subject signs informed consent, meets all inclusion and none of the exclusion criteria, and the Heart Team determines the subject is suitable for randomization in the trial, then the subject is reviewed by the Screening Committee. If the subject is approved by the Screening Committee and the subject is randomized to either TAVR or SAVR, the subject is added to the randomized population. Within the randomized population the following analysis sets are distinguished:

- **The intention to treat (ITT) set:** Subjects are reported according to the randomized assignment, SAVR or TAVR, regardless of what, if any, therapy was actually received.
- **The as treated (AT) set:** The AT set consists of all ITT subjects with an attempted implant procedure, defined as when the subject is brought into the procedure room and any of the following have occurred: anesthesia administered, vascular line placed, TEE placed or any monitoring line placed. Subjects will be analyzed according to their first attempted procedure (TAVR or SAVR).
- **The implanted set:** The Implanted set consists of all the AT subjects who are actually implanted with either the TAV or SAV.
- **The per protocol (PP) set:** The PP set will be defined based on the ICH E9 Statistical Principles, and will be specified in the statistical analysis plan (SAP).

The primary analysis for the primary objective, secondary safety objectives, secondary effectiveness objectives (except for valve dysfunction, hemodynamic performance metrics, and device success) will use the AT set. Valve dysfunction, hemodynamic performance metrics, and device success will use the implanted set.

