8. Subjects confirmed eligible for implantation by the Screening Committee will be randomized in a 1:1 fashion to either TAVR or SAVR, stratified by site and the need for coronary revascularization during SAVR. Coronary artery bypass graft (CABG) should be conducted during the index procedure. Concomitant percutaneous coronary intervention (PCI)v and TAVR is encouraged; however staging is left to the discretion of the operator. Intervention/repair of the mitral and/or tricuspid valve is only

---

iiiIf a subject has balloon aortic valvuloplasty after their qualifying TTE, they must have repeat TTE to confirm he/she meets criteria for severe aortic stenosis as described in Section 3.3.5.1 prior to submission to the screening committee.

[figure not shown]
iv Anatomical suitability will be confirmed by Medtronic Screening Lab. Information on MDCT procedures and sizing recommendations is provided in Appendix II, Section 4.0.

v Index PCI should be performed at the TAVR implanting center; index PCI operators will be considered investigators.

allowed if deemed necessary during the SAVR procedure, but there must be no intent to do this type of intervention/repair prior to implant.

9. Trial randomization will not be blinded. Once randomization is complete and a treatment arm is assigned, crossover from SAVR to TAVR treatment is not permitted. The sponsor will strictly monitor device dispensation to ensure that only those subjects randomized to the Medtronic TAVR treatment arm receive the Medtronic TAV. Distribution of the subjects within the trial groups will be controlled at the implanting sites by means of central randomization using interactive voice/web randomization service (IXRS). The randomization scheme will be securely stored at the IXRS provider.
10. Implantation should occur within 90 days of Screening Committee approval.
11. Subjects who consent to participate in the LTI study will also follow the LTI sub-study protocol as described in APPENDIX VII: LEAFLET THICKENING/IMMOBILITY SUB-STUDY PROTOCOL

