**3.3.11 Subject Disposition**

Sites will maintain a log of subjects consented, his/her assigned treatment group, date attempted and implanted, as well as the Subject ID numbers assigned to each patient. Subjects who are consented but are not taken to the procedure room for implantation will be exited from the trial, and will not be followed beyond the date of trial exit.

Subjects who are taken to the procedure room for implantation but do not receive a TAV or surgical valve for any reason will be followed for the trial duration. Subjects that have their TAV or SAVR bioprosthesis explanted will be followed for the trial duration.

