## 6.6. Description of Performed Analysis, per Population

The primary analysis for the primary endpoint will be performed on the AT set. In addition, it will also be performed on the ITT, Implanted, and PP sets. The inferential statistics for the following secondary endpoints will be performed on the AT set:

- The rate of the composite of death, disabling stroke, life-threatening bleed, major vascular complications, or AKI (II or III) at 30 days
- The rate of new permanent pacemaker implantation at 30 days
- The rate of prosthetic valve endocarditis at one year
- The rate of prosthetic valve thrombosis at one year
- The rate of all stroke (disabling and non-disabling) at one year
- The rate of life-threatening bleeding at one year
- The rate of valve-related dysfunction requiring repeat procedure at one year
- Quality of Life as assessed by Kansas City Cardiomyopathy Questionnaire (KCCQ) at one year
- The rate of repeat hospitalization for aortic valve disease at one year
- New York Heart Association (NYHA) functional classification at 30 days, 6 months, one year, 18 months, 2 years, 3 years, 4 years, 5 years, 7 years and 10 years
- Health-related quality of life at one year as assessed by EQ-5D survey instrument

The implanted set will be used for analyzing the primary endpoint, secondary endpoint of prosthetic valve dysfunction, device success, and echocardiographic assessment of valve performance.

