**Confidential**

All of the above non-inferiority will be tested with a type I error standard of 0.05 and superiority tests will be tested with a type I error standard of 0.025. If all of the above tests meet their success criterion, the primary endpoint (superiority) will be tested using a type I error rate of 0.025.

For the purposes of seeking claims, these objectives will only be evaluated once, at the same time as non-inferiority of the primary objective is established. The only exception to this is the primary endpoint superiority test, which carries the possibility of a delayed determination of superiority and may thus meet its success criterion at a different time (see Section 6.5.2).

The remaining secondary endpoints (see Section 3.2 and Section 3.3) may be of interest for scientific reasons but will not be the basis for supporting labeling claims; they are thus outside of the hierarchical testing procedure. Similarly, for those objectives that test non-inferiority, if non-inferiority is established, a test of superiority may also be conducted, but unless specifically itemized in the list, such superiority testing is not part of the hierarchical testing procedure; these superiority tests may be of interest for scientific reasons but will not be the basis for supporting labeling claims.

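### The primary decisions group attempted subjects by first attempted procedure, so TAVR-assigned subjects taken first to surgery count as SAVR; the comparison is not a randomised one and can be biased in either direction

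*Protocol*

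**What the plan says.** Protocol 3.3.3.2.2 and SAP 6.2.2 admit a randomised subject to the AT set once there is an attempted procedure, "defined as when the subject is brought into the procedure room and any of the following have occurred": anaesthesia, or placement of a vascular line, TEE probe or monitoring line. On arm membership, both say: "Subjects will be analyzed according to their first attempted procedure (TAVR or SAVR".

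SAP 6.6 states: "The primary analysis for the primary endpoint will be performed on the AT set". It then adds: "In addition, it will also be performed on the ITT, Implanted, and PP sets". The primary superiority test concerns the same endpoint. Under SAP 6.9, once the seven ordered secondary tests have passed, "the primary endpoint (superiority) will be tested using a type I error rate of 0.025". No other analysis set is named for it.

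On crossover, item 9 of Protocol 3.3.8 says: "Once randomization is complete and a treatment arm is assigned, crossover from SAVR to TAVR treatment is not permitted". The sponsor enforces this by monitoring who is dispensed the Medtronic valve. The same item says the allocation is not blinded. Nothing equivalent covers a TAVR-assigned subject who goes to surgery.

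Under Protocol 3.3.11, consented subjects who never reach the procedure room are exited and not followed. By contrast, "Subjects who are taken to the procedure room for implantation but do not receive a TAV or surgical valve" stay in follow-up for the whole trial.

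**The concern.** An arm defined by what was first attempted can depend on events after an open-label assignment. Protocol 3.3.8 aims for implantation within 90 days of Screening Committee approval, which leaves time for a subject's condition or plan to change. If a TAVR-assigned subject is sent to surgery before a TAVR attempt starts, that subject and any death or disabling stroke move from the TAVR column to the SAVR column.

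So the comparison behind both the non-inferiority decision and a possible superiority label claim loses the protection of randomisation for those subjects. The restriction on crossover is also asymmetric, because only the SAVR-to-TAVR route is closed. If the moved subjects are sicker than average, the TAVR rate falls and the SAVR rate rises together.

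**Working it through.** **Who is moved.** Four cases follow from Protocol 3.3.3.2.2, 3.3.8 and 3.3.11.

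- TAVR-assigned, TAVR attempt begun, later converted to surgery: stays in TAVR.
- TAVR-assigned, no attempt of any kind: not in AT.
- TAVR-assigned, surgery attempted first: counted as SAVR.
- SAVR-assigned, TAVR attempted first: would be counted as TAVR, but this is prohibited and could arise only as a deviation.

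**Whether another planned set isolates the third case.** None does.

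- ITT keeps randomised arms, but it adds never-attempted subjects with no follow-up, whose 24-month outcomes must be predicted by the model in SAP 6.5.2. It also starts the clock at randomisation instead of at the procedure.
- The PP set requires implantation as randomised, so it drops switchers.
- The Implanted set is a subset of AT, and SAP 6.2.2 gives no rule that returns its members to their randomised arm.

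The missing analysis is attempted subjects by randomised arm.

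**The plan's own figure.** Protocol 3.3.3.4.3 gives 1032 for a single look: rates 0.15 and 0.15, margin 0.06, alpha 0.05, power 85%, Farrington-Manning. The restricted estimates under the null are 0.1848 and 0.1248.

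- s0 = √(0.1848×0.8152 + 0.1248×0.8752) = 0.5098
- s1 = √(2×0.15×0.85) = 0.5050
- n per arm = [(1.645×0.5098 + 1.036×0.5050)/0.06]² ≈ 515.2, so 516 per arm and 1032 in total

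This matches exactly and shows that alpha is one-sided 0.05 (one-sided 0.025 would give 1288). Crossover does not enter the formula, so regrouping leaves 1032, 1100 and 1200 unchanged.

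**Effect of moving subjects.** From the documents: 1200 AT subjects at 1:1, taken as N = 600 per arm; SAVR rate 0.15; margin 0.06. Assumed, because the documents do not give them: the share x of TAVR-assigned subjects moved, and their 24-month event risk q. As-randomised rates pT and pC are held fixed, and m = xN.

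- AT TAVR rate = (N·pT − m·q)/(N − m)
- AT SAVR rate = (N·pC + m·q)/(N + m)
- D = AT TAVR rate − AT SAVR rate, with SE the unpooled standard error of D
- False non-inferiority (pT = 0.21, pC = 0.15) = Φ[(0.06 − D)/SE − 1.645]
- False superiority (pT = pC = 0.15) = Φ[−D/SE − 1.960]

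Worked case, x = 1% and q = 40%: m = 6, carrying 2.4 events.

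- At the margin: TAVR = (126 − 2.4)/594 = 0.2081; SAVR = (90 + 2.4)/606 = 0.1525; D = 0.0556; SE = 0.0221; error = Φ(−1.446) = 7.4%.
- With equal arms: 87.6/594 = 0.1475 and 92.4/606 = 0.1525; D = −0.0050; SE = 0.0206; error = Φ(−1.717) = 4.3%.

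| x | q | shift at margin (points) | non-inferiority error | shift, equal arms (points) | superiority error |
|---|---|---|---|---|---|
| 1% | 10% | +0.16 | 4.3% | +0.10 | 2.2% |
| 1% | 15% | +0.06 | 4.7% | 0.00 | 2.5% |
| 1% | 18% | 0.00 | 5.0% | −0.06 | 2.7% |
| 1% | 30% | −0.24 | 6.2% | −0.30 | 3.5% |
| 1% | 40% | −0.44 | 7.4% | −0.50 | 4.3% |
| 2% | 10% | +0.32 | 3.7% | +0.20 | 2.0% |
| 2% | 40% | −0.88 | 10.6% | −1.00 | 7.0% |

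Negative shifts favour TAVR.

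**Break-even.** Setting the shift to zero gives q = [pT(1 + x) + pC(1 − x)]/2. With x = 1% at the margin this is (0.2121 + 0.1485)/2 = 0.180. With equal arms at 0.15 it is 0.15.

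**The case against.** A reader might infer that relabelling can run one way only and must therefore favour TAVR. The documents do not support that. The AT rule itself is symmetric. Protocol 3.3.8 says "crossover from SAVR to TAVR treatment is not permitted", but a prohibition does not rule out deviations: unauthorised device use is a listed example in 3.3.18, and 4.5 lists TAVR with another device, which the sponsor's supply control does not reach. The protocol is silent on TAVR-to-SAVR and does not expressly allow it.

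The affected group is also narrow. The Screening Committee confirms anatomy for both procedures before randomisation (Protocol 3.2.3), and a TAVR attempt that has begun stays in TAVR. At 0.5–2% of 600, only 3–12 subjects would move. They must have been accepted for open surgery, in a trial limited to predicted 30-day operative mortality below 3%, so high event risk cannot be presumed. A switch for access anatomy or preference implies no excess risk.

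ITT keeps switchers in their randomised arm and PP removes them, so a large effect would probably show as a discrepancy between sets. The error rates above are not those of the trial, whose thresholds are calibrated by simulation for several looks and are not stated in these documents. The superiority figures also assume that non-inferiority and all seven gatekeeping tests have passed.

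All of this stands, and it limits the size and removes the fixed direction. It does not make the decision comparison a randomised one, and it does not supply the missing analysis. The usual defence of as-treated grouping in non-inferiority, that as-randomised analysis dilutes a true difference, is weak at this scale: 0.5–2% of a 6-point difference is 0.03–0.12 points.

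**Conclusion.** The concern holds in a limited form. The primary non-inferiority and superiority decisions rest on arms defined by first attempted procedure, with only the SAVR-to-TAVR route closed, and no planned analysis takes attempted subjects by randomised arm. This can bias the comparison: towards TAVR if moved subjects' 24-month risk exceeds about 18% at the margin or 15% with equal arms, and against TAVR below that.

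The size is unknown, because the documents give neither the share moved nor the risk. In the illustration, 1% moved takes non-inferiority error to between 4.3% (10% risk) and 7.4% (40% risk), and superiority error to between 2.2% and 4.3%. These are single-look normal approximations with 600 per arm and thresholds of 0.95 and 0.975. They are not operating characteristics of the trial's Bayesian multi-look design.

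The documents do not show that the rule favours TAVR, or that TAVR-assigned subjects found unsuitable are generally counted as SAVR. Only those taken to surgery before any TAVR attempt begins are moved. This is a cheap improvement and does not by itself invalidate the design.

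**What to change.** In Protocol 3.3.3.2.2 and SAP 6.2.2 and 6.6:

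- Keep the attempted-procedure rule for entry to the set.
- Run the primary superiority test on attempted subjects grouped by randomised assignment.
- For non-inferiority, keep AT as the decision set. Pre-specify the posterior probability for attempted subjects by randomised arm as a key sensitivity analysis, reported beside the AT result.
- List every subject whose first attempted procedure differs from assignment, by arm and reason.

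Replacing AT as the only non-inferiority set, or requiring both groupings to pass, goes further and is a trade-off on which statisticians would differ; this point does not depend on it.

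The cost is wording in two documents and one grouping variable. Attempted subjects are already followed under Protocol 3.3.11, so no new data and no change in sample size are needed. The downside is that a few TAVR-assigned surgical patients stay in the TAVR arm, which slightly dilutes the device-specific estimate.
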